## 16.2 ASA physical status (PS) classification - Current Definitions and ASA-Approved Examples [54]

ASA PS Classification	Definition	Adult examples, including, but not limited to:	Pediatric examples, including but not limited to:	Obstetric examples, including but not limited to:
ASA I	A normal healthy patient	Healthy, non-smoking, no or minimal alcohol use	Healthy (no acute or chronic disease), normal BMI percentile for age	
ASA II	A patient with mild systemic disease	Mild diseases only without substantive functional limitations. Current smoker, social alcohol drinker, pregnancy, obesity ( $30 < \text{BMI} < 40$ ), well-controlled DM/HTN, mild lung disease.	Asymptomatic congenital cardiac disease, well controlled dysrhythmias, asthma without exacerbation, well controlled epilepsy, non-insulin dependent diabetes mellitus, abnormal BMI percentile for age, mild/moderate OSA, oncologic state in remission, autism with mild limitations.	Normal pregnancy*, well controlled gestational HTN, controlled preeclampsia without severe features, diet-controlled gestational DM.
ASA III	A patient with severe systemic disease	Substantive functional limitations; One or more moderate to severe diseases. Poorly controlled DM or HTN, COPD, morbid obesity ( $\text{BMI} \geq 40$ ), active hepatitis, alcohol dependence or abuse, implanted pacemaker, moderate reduction of ejection fraction, ESRD undergoing regularly scheduled dialysis, history ( $>3$ months) of MI, CVA, TIA, or CAD/stents.	Uncorrected stable congenital cardiac abnormality, asthma with exacerbation, poorly controlled epilepsy, insulin dependent diabetes mellitus, morbid obesity, malnutrition, severe OSA, oncologic state, renal failure, muscular dystrophy, cystic fibrosis, history of organ transplantation, brain/spinal cord malformation, symptomatic hydrocephalus, premature infant PCA $<60$ weeks, autism with severe limitations, metabolic disease, difficult airway, long term parenteral nutrition. Full term infants $<6$ weeks of age.	Preeclampsia with severe features, gestational DM with complications or high insulin requirements, a thrombophilic disease requiring anticoagulation.

ASA PS Classification	Definition	Adult examples, including, but not limited to:	Pediatric examples, including but not limited to:	Obstetric examples, including but not limited to:
ASA IV	A patient with severe systemic disease that is a constant threat to life	Recent (<3 months) MI, CVA, TIA or CAD/stents, ongoing cardiac ischemia or severe valve dysfunction, severe reduction of ejection fraction, shock, sepsis, DIC, ARD or ESRD not undergoing regularly scheduled dialysis.	Symptomatic congenital cardiac abnormality, congestive heart failure, active sequelae of prematurity, acute hypoxic-ischemic encephalopathy, shock, sepsis, disseminated intravascular coagulation, automatic implantable cardioverter-defibrillator, ventilator dependence, endocrinopathy, severe trauma, severe respiratory distress, advanced oncologic state.	Preeclampsia with severe features complicated by HELLP or other adverse event, peripartum cardiomyopathy with EF <40, uncorrected/decompensated heart disease, acquired or congenital.
ASA V	A moribund patient who is not expected to survive without the operation	Ruptured abdominal/thoracic aneurysm, massive trauma, intracranial bleed with mass effect, ischemic bowel in the face of significant cardiac pathology or multiple organ/system dysfunction.	Massive trauma, intracranial hemorrhage with mass effect, patient requiring ECMO, respiratory failure or arrest, malignant hypertension, decompensated congestive heart failure, hepatic encephalopathy, ischemic bowel or multiple organ/system dysfunction.	Uterine rupture.
ASA VI	A declared brain-dead patient whose organs are being removed for donor purposes			

\* Although pregnancy is not a disease, the parturient's physiologic state is significantly altered from when the woman is not pregnant, hence the assignment of ASA 2 for a woman with uncomplicated pregnancy.

The addition of "E" denotes Emergency surgery: (An emergency is defined as existing when delay in treatment of the patient would lead to a significant increase in the threat to life or body part).

1.0 INTRODUCTION

1.1 Background and Rationale

A 2009 study of obstetric anesthesia practice found four deaths due to administration of tranexamic acid into the neuraxis. Errors of this type are referred to as misconnections or wrong-route drug delivery. This 2009 study is just one example of death or serious harm that can result from wrong-route drug delivery. Misconnections are often the result of accidental administration of substances, that are safe to deliver intravascularly, via the neuraxial route.

Authors across disciplines have concluded that the mortality and morbidity associated with such errors is secondary to the universal adoption of Luer lock equipment.

Furthermore, sentinel interest groups in the US and the EU have issued warnings about the risk of universal Luer connectors, that allow these misconnections. Therefore, implementation of devices with non-Luer connectors could improve patient safety and decrease the risk of misconnections.

The goal of the ISO 80369 standard for Small Bore Connectors is to reduce the risk of misconnections between medical devices or between accessories for different applications. ISO 80369-6:2016 specifies requirements for small bore connectors intended to be used for connections in neuraxial applications. Neuraxial applications involve the use of medical devices intended to administer medications to neuraxial sites, wound infiltration anesthesia delivery, other regional anesthesia procedures and monitoring or removing cerebrospinal fluid for therapeutic or diagnostic purposes. The neuraxial ISO 80369-6 devices have been designated as NRFit. They are visually identifiable by an NRFit label and yellow device components, both of which denote that the device is only for neuraxial use.

BD manufactured ISO 80369-6 compliant devices from medication preparation to delivery, such as the spinal NRFit™ needles, the spinal introducer NRFit™ needles, the spinal NRFit™ needle sets, the syringes NRFit™, the blunt fill and blunt filter NRFit™ needles.

This study is designed to assess the safety and performance of the BD Spinal NRFit™ Needles, BD Spinal NRFit™ Needle Sets, BD Spinal Introducer NRFit™ Needles, BD Syringes NRFit™ devices, mainly, but not limited to the purpose of providing clinical data required under European Union (EU) regulation 2017/745.

1.2 Objectives and Endpoints

THIS SUBJECT MATTER IS RESTRICTED SOLELY FOR THE USE OF BECTON DICKINSON AND COMPANY AND ITS SUBSIDIARIES

 BD	Statistical Analysis Plan	Page No.
	Study ID: MDS-21NRFit001	Version No: 1.0

GFM-10082C

Table 1. Objectives and Endpoints

Objective Types	Objectives	Endpoints
Primary Performance	
 To assess the performance of the BD Spinal NRFit™ needles and BD NRFit™ introducers used in spinal anesthesia procedures. To assess the performance of BD NRFit™ Syringes when used in spinal anesthesia procedures. 	
 Percentage of participants with successful placement of the BD Spinal NRFit™ needle in the subarachnoid location defined as the spontaneous appearance of cerebrospinal fluid (CSF) emerging from the spinal needle hub. Percentage of participants with successful placement of the BD Spinal NRFit™ needle in the subarachnoid location defined as the spontaneous appearance of cerebrospinal fluid (CSF) emerging from the spinal needle hub when an BD NRFit™ introducer is used. Percentage of participants with successful aspiration and injection of anesthetic through a BD NRFit™ Syringe. Percentage of participants with BD NRFit™ Syringes that do not leak at the connection point during medication administration.
Primary Safety	
 To assess the incidence of post dural puncture headache (PDPH) 	
 Percentage of participants with a diagnosis of PDPH (defined as headache that worsens when standing/upright position and relieves when laying supine) for a period of up to 10 (± 3 days) days following the procedure.

THIS SUBJECT MATTER IS RESTRICTED SOLELY FOR THE USE OF BECTON DICKINSON AND COMPANY AND ITS SUBSIDIARIES

 BD	Statistical Analysis Plan	Page No.
	Study ID: MDS-21NRFit001	3 of 13

GFM-10082C

	
 • To assess the incidence of any BD NRFit™ spinal needle and BD NRFit™ introducer and BD NRFit™ syringe and procedure-related adverse events (other than PDPH) 	
 • Incidence of device/procedure-related adverse events
--	--	--

1.3 Acceptance Criteria and/or Investigation Hypothesis

Observed data in line with literature data:

- Successful needle placement $\geq 90\%$
- Incidence of PDPH $\leq 3\%$
- Incidence of misconnection 0%
- Incidence of medication leak at BD NRFit™ syringe connection point $< 2\%$
- Incidence of aspiration/injection through a BD NRFit™ syringe $> 80\%$

2.0 STUDY DESIGN

2.1 Study Design

This is a multi-center, prospective, open label, single arm post-market study that will enroll approximately 180 participants in order to have a minimum of 150 treated participants who will receive a spinal anesthesia procedure as part of their routine medical care. A minimum of 50 participants for each of the two needle tip types (Quincke and Whitacre tip) will be enrolled in the study. Data related to the safety and performance of the BD Spinal NRFit™ Needles, the BD Spinal Introducer NRFit™ Needles, the BD Spinal NRFit™ Needle Sets, the BD Syringes NRFit™ and ancillary devices will be captured when used as intended.

Participants will be screened against eligibility criteria and will be considered enrolled once the informed consent document is signed. The procedure(s) performed, and device(s) used, will be left to the discretion of the participant's physician investigator.

Participants will be followed from the time of spinal procedure for up to 10 days (± 3 days) post spinal procedure to assess for any adverse events/complications.

A participant is considered to have completed the study if he/she has completed all phases of the study including the day-10 (± 3 days) post procedure follow-up assessment.

The end of the study is defined as the date of the last study assessment of the last participant in the study.

2.2 Study Population

Participants will be recruited from the patient population treated at the investigational sites. Sites may choose to limit recruitment to specific areas of the hospital and/or to patients treated by specific healthcare providers.

THIS SUBJECT MATTER IS RESTRICTED SOLELY FOR THE USE OF BECTON DICKINSON AND COMPANY AND ITS SUBSIDIARIES

 BD	Statistical Analysis Plan	Page No.
	Study ID: MDS-21NRFit001	4 of 13

GFM-10082C

2.2.1 Inclusion Criteria

In order to be eligible to participate in this study, an individual must meet all of the following criteria:

1. Any patient, regardless of age or gender, for which the investigator has decided that a neuraxial procedure must be performed utilizing BD NRFit™ Spinal Needles, NRFit™ Spinal Introducer Needles, and NRFit™ Syringes as part of their routine medical care.
2. Expected to be available for observation through the study period (10 days, \pm 3 days, post procedure*).
3. Able and willing to provide signed and dated informed consent or legal authorized representative (LAR) authorized to give consent on behalf of the participant (Note: Consent of guardian or parent may be required for participants under the age of 18 years; participant assent may be required as well).

**The time window of \pm 3 days must be used when the 10-day post-procedure occurs during the weekends or holidays.*

2.2.2 Exclusion Criteria

Participants are excluded from the study if any of the following criteria apply:

1. Coagulopathy or bleeding disorder, where it is in the opinion of the investigator makes regional anesthetic of increased risk.
2. Subjects with a history of neurological impairment of the trunk or lower extremities.
3. Infection at the site of needle insertion.
4. Previous spine surgery at the level involved in the study procedure.

2.3 Randomization and Blinding

This is a single-arm and open label study, randomization and blinding are not applicable.

2.4 Sample Size

The planned sample size is approximately 150 subjects treated with BD NRFit™ Spinal Needle and BD NRFit™ Syringe, and approximately 100 subjects treated with BD NRFit™ Spinal Introducer. The sample size is based on the precision of endpoint estimates as well as the ability to detect adverse events. For a given endpoint with 90% rate, a sample size of 150 would lead to a precision of 4.8%, a sample size of 100 would lead to a precision of 6.0%. Table 2 below contains further detail. For an adverse event with 1% rate, there is a probability of 77.9% to observe at least 1 event in a sample of 150.

 BD	Statistical Analysis Plan	Page No.
	Study ID: MDS-21NRFit001	5 of 13

GFM-10082C

Table 2. Sample Size and Precision

Sample Size	Rate	Precision (Half width of 95% CI)
150	90%	4.80%
100	90%	6.00%
150	80%	6.40%
150	3%	3.10%
150	2%	2.70%

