4.0 ANALYSIS POPULATION SET(S)

4.1 Populations Definitions

The following populations are defined in the table below:

Table 4. Population Definitions

Population	Description
Enrolled	All participants who sign the ICF
Treated	All participants in whom a spinal anesthesia procedure is attempted, regardless of success
Safety	All participants in whom a spinal anesthesia procedure is successful

Treated population will include the following participants on the Spinal Procedure CRF page:

- 'Was spinal procedure performed or attempted using BD NRFit devices?' Equals 'Yes'.

Safety population will include the following participants on the Spinal Procedure Details - BD NRFit Needle CRF page:

- 'Was there a spontaneous appearance of cerebrospinal fluid (CSF) emerging from the needle hub?' Equals 'Yes'.

The primary performance endpoints analysis will be performed on the treated population. The primary safety endpoint analysis for PDPH incidence will be performed on the safety population. The primary safety endpoint analysis for device/procedure-related adverse events (other than PDPH) will be performed on the treated population.

THIS SUBJECT MATTER IS RESTRICTED SOLELY FOR THE USE OF BECTON DICKINSON AND COMPANY AND ITS SUBSIDIARIES

 BD	Statistical Analysis Plan	Page No.
	Study ID: MDS-21NRFit001	7 of 13

GFM-10082C

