5.2.1.2 Performance of the BD NRFit™ Syringes

- Rate of successful aspiration of anesthetic through BD NRFit™ Syringes

A subject will be included in the analysis population if the following condition is met:

- Spinal Procedure Details – Syringe CRF page: 'Was a BD syringe NRFit used?' Equals 'Yes'

A successful aspiration of anesthetic through BD NRFit™ Syringe is defined as follows:

- 'Was anesthetic medication successfully aspirated through the BD NRFit syringe?' Equals 'Yes'

The incidence rate for this endpoint will be calculated as the number of participants experiencing the event divided by the total number of treated participants using the BD NRFit™ Syringes; 95% confidence interval (exact method) will be calculated.

- Rate of successful injection of anesthetic through BD NRFit™ Syringes

A subject will be included in the analysis population if the following condition is met:

- Spinal Procedure Details – Syringe CRF page: 'Was a BD syringe NRFit used?' Equals 'Yes'

A successful injection of anesthetic through BD NRFit™ Syringe is defined as follows:

- 'Was anesthetic medication successfully injected through the BD Syringe NRFit?' Equals 'Yes'

The incidence rate for this endpoint will be calculated as the number of participants experiencing the event divided by the total number of safety population using the BD NRFit™ Syringes; 95% confidence interval (exact method) will be calculated.

 BD	Statistical Analysis Plan	Page No.
	Study ID: MDS-21NRFit001	9 of 13

GFM-10082C

- Rate of BD NRFit™ Syringes that do not leak at the connection point during medication administration
A subject will be included in the analysis population if the following condition is met:
 - Spinal Procedure Details – Syringe CRF page: 'Was a BD syringe NRFit used?' Equals 'Yes'
A success of the endpoint for the BD NRFit™ Syringe is defined as follows:
 - 'Did the BD Syringe NRFit leak at the connection point during medication administration?' Equals 'No'

The incidence rate for this endpoint will be calculated as the number of participants experiencing the event divided by the total number of safety population using the BD NRFit™ Syringes; 95% confidence interval (exact method) will be calculated.

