5.2.2 Primary Safety Endpoints

- Incidence of post dural puncture headache (PDPH)

The event of PDPH is defined as headache that worsens when standing/upright position and relieves when laying supine for a period of up to 10 (\pm 3 days) days following the procedure.

The incidence of PDPH will be based on response to the following question:

- "Post-dural Puncture Headache" CRF page: "Did the subject develop post-dural puncture headache (PDPH)?" Equals 'Yes'

Participants experiencing any severity (mild/moderate/severe) of PDPH will contribute to the incidence count in the numerator.

The incidence rate for the above primary safety endpoints will be calculated as the number of participants experiencing the event divided by the total number of safety participants defined in section 4.1; 95% confidence interval (exact method) will be calculated.

- Incidence of any BD NRFit™ spinal needle and BD NRFit™ introducer and BD NRFit™ syringe and procedure-related adverse events (other than PDPH)

Subject will be considered as having an event if the subject has the following responses for the questions on the AE CRF Page listed below:

THIS SUBJECT MATTER IS RESTRICTED SOLELY FOR THE USE OF BECTON DICKINSON AND COMPANY AND ITS SUBSIDIARIES

 BD	Statistical Analysis Plan	Page No.
	Study ID: MDS-21NRFit001	10 of 13

GFM-10082C

- Relationship to procedure: Equals 'Possible' or 'Probable' or 'Causal' OR
Relationship to spinal needle: Equals 'Possible' or 'Probable' or 'Causal'
OR Relationship to syringe: Equals 'Possible' or 'Probable' or 'Causal' OR
Relationship to introducer: Equals 'Possible' or 'Probable' or 'Causal'

The incidence rate for the above primary safety endpoints will be calculated as the number of participants experiencing the event divided by the total number of treated participants; 95% confidence interval (exact method) will be calculated.

THIS SUBJECT MATTER IS RESTRICTED SOLELY FOR THE USE OF BECTON DICKINSON AND COMPANY AND ITS SUBSIDIARIES

 BD	Statistical Analysis Plan	Page No.
	Study ID: MDS-21NRFit001	11 of 13

GFM-10082C

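### The 3.1% precision stated at a 3% rate is computed on 150 treated participants, but PDPH is analysed in the smaller CSF-positive safety population (minor)

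*SAP*

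**What the plan says.** **Sample size.** SAP 2.4 and Protocol 10.2 base the sample size on the precision of the endpoint estimates and on the chance of seeing an adverse event. SAP 2.4: "The planned sample size is approximately 150 subjects treated with BD NRFit™ Spinal Needle and BD NRFit™ Syringe". The precision table (Protocol Table 1, SAP Table 2) lists 3.1% at n=150 and a 3% rate, and 2.7% at n=150 and a 2% rate. The rows carry no endpoint names. The two rates equal the acceptance limits for PDPH (at most 3%) and syringe leak (below 2%) in Protocol 3.1 and SAP 1.3.

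**Enrolment.** SAP 2.1 says the study "will enroll approximately 180 participants in order to have a minimum of 150 treated participants", so 150 treated is a floor.

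**PDPH denominator.** SAP 5.2.2 has the count "divided by the total number of safety participants defined in section 4.1". SAP 4.1 defines the safety population as "All participants in whom a spinal anesthesia procedure is successful" and identifies it by a Yes to the CRF question on spontaneous appearance of CSF. Protocol 10.3 and 10.5.2 use the same population.

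**Leak denominator.** SAP 5.2.1.2 has the no-leak count "divided by the total number of safety population using the BD NRFit™ Syringes". Protocol 10.3 and 10.5.1.2, and the general statement in SAP 4.1, place the performance endpoints on the treated population.

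**The concern.** The safety population is a subset of the treated population, so the 3% row is computed on a different and larger group than the one PDPH will be estimated in. The table makes no allowance for failed placements, although the plan's own criterion would accept up to 10% of them.

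There is no power calculation or hypothesis test. The table is therefore the main justification of the sample size, and PDPH is a primary safety endpoint. At stake is whether the precision quoted for it is the precision the planned analysis gives.

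**Working it through.** **Inputs.** Treated minimum 150 (SAP 2.1); rates 3% and 2% (SAP Table 2); two-sided 95% exact interval (SAP 5.2.1.2 and 5.2.2); placement acceptance floor 90% (SAP 1.3). Placement of 95% is my assumption, to show the range.

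**Formula.** With x = n × rate, the Clopper-Pearson limits are L = Beta quantile(0.025; x, n−x+1) and U = Beta quantile(0.975; x+1, n−x). Half-width = (U − L)/2.

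**Reproducing the plan's figures at n=150.**
- 3%: x = 4.5. The limits lie 4.15 points above and 2.09 points below the rate, so the half-width is (4.15 + 2.09)/2 = 3.12, stated as 3.1.
- 2%: x = 3. (3.73 + 1.59)/2 = 2.66, stated as 2.7.

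Of the usual intervals, only the exact one matches both rows. Wald gives 2.73 and 2.24, Wald with continuity correction 3.06 and 2.57, and Wilson 2.94 and 2.52.

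**Size of the safety population from 150 treated.** At 90% placement, 150 × 0.90 = 135. At 95%, 150 × 0.95 = 142.5, about 143.

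**PDPH row (3%) on that population.**

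| Safety n | Half-width | Upper limit |
|---|---|---|
| 150 | 3.12% | 3 + 4.15 = 7.15% |
| 148 | 3.15% (3.146) | 3 + 4.19 = 7.19% |
| 147 | 3.16% (3.158) | 3 + 4.21 = 7.21% |
| 143 | 3.21% | 3 + 4.29 = 7.29% |
| 135 | 3.32% | 3 + 4.46 = 7.46% |

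The figure still rounds to 3.1% at n=148 but not at n=147. With exactly 150 treated this requires 148/150 = 98.7% of them in the safety population.

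**Treated number that restores 3.1% at 90% placement.** 150/0.90 = 166.7, so 167, giving 167 × 0.90 = 150.3 safety participants on average. If all 180 were treated, 180 × 0.90 = 162, with a half-width of 2.99%.

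**Leak row (2%).** On 150 treated the stated 2.7% stands (2.66). If the safety population is kept and every safety participant used the syringe, n=143 gives 2.74, which still rounds to 2.7%, and n=135 gives 2.83, or 2.8%.

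**The case against.** The table correctly states what n=150 yields, its rows are unlabelled, and the sample is only approximately 150. The 90% figure is an acceptance floor, not a planned placement rate. Success is judged on the last attempt and more than one needle may be used, so actual placement could be well above 90%. The treated number is a minimum. The shift is also smaller than the effect of one event: 4 of 150 gives a half-width of 2.98 and 5 of 150 gives 3.26, a difference of 0.28 points.

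All of this stands, and it limits the size of the point. It does not remove the mismatch: every statement about PDPH in both documents names the safety population, and the row that matches PDPH uses the treated number.

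A reader might infer more in three ways.
- **That the trial will fail to deliver its stated precision.** This needs treated numbers near the minimum together with too many failed placements; about 167 treated removes the shortfall even at 90%.
- **That loss to follow-up is ignored and widens the interval further.** Protocol 10.4 does analyse evaluable data only, but Protocol 8.1 allows replacement of participants who leave before the day-10 follow-up, and neither document gives a loss rate. I therefore put no figure on it.
- **That the leak row has the same error.** Only SAP 5.2.1.2 uses the safety population for leak. The prior question there is which denominator applies.

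**Conclusion.** The point holds for PDPH and is minor. At the minimum of 150 treated, the half-width is 3.2% at 95% placement and 3.3% at the 90% floor, against 3.1% stated. The largest shift is 3.32 − 3.12 = 0.20 points, and the upper limit moves from 7.15% to 7.46%. This assumes exactly 150 treated, placement at or above the acceptance floor, and a PDPH answer for every safety participant.

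The documents do not support reading this as a sample-size failure. SAP 1.3 compares observed rates with the limits and sets no confidence-limit test, so no acceptance decision changes and no extra enrolment is called for. For leak, nothing is established until the denominators are reconciled: 2.7% is right on the treated population, and 2.8% applies only at n=135 in the safety population.

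**What to change.** 1. In Protocol Table 1 and SAP Table 2, label the 3% row as PDPH in the safety population. Restate it as 3.3% at n=135, with the range 3.1% to 3.3% for n from 150 down to 135. Alternatively, keep 3.1% and state that it requires 150 safety participants, which is about 167 treated at 90% placement.
2. Reconcile the leak denominator between Protocol 10.3 and 10.5.1.2 and SAP 4.1 (treated) and SAP 5.2.1.2 (safety). Then label the 2% row: 2.7% if treated, 2.8% at n=135 if safety.
3. Add a column naming the endpoint and analysis population for every row. While the table is open, check the interval method in the other rows: 4.8%, 6.0% and 6.4% match Wilson (4.84, 5.96, 6.37), whereas the planned exact method gives 5.13, 6.36 and 6.69.

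The cost is wording and table entries in two documents, with slightly less favourable stated precision. Enrolment, data collection and the PDPH analysis are unchanged.

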### 10.2 Sample Size Considerations

The planned sample size is approximately 150 subjects treated with BD NRFit™ Spinal Needle and BD NRFit™ Syringe, and approximately 100 subjects treated with BD NRFit™ Spinal Introducer. The sample size is based on the precision of endpoint estimates as well as the ability to detect adverse events. For a given endpoint with 90% rate, a sample size of 150 would lead to a precision of 4.8%, a sample size of 100 would lead to a precision of 6.0%. Table 1 below contains further detail. For an adverse event with 1% rate, there is a probability of 77.9% to observe at least 1 event in a sample of 150.

Table 1: Sample Size and Precision

Sample Size	Rate	Precision (Half width of 95% CI)
150	90%	4.8%
100	90%	6.0%
150	80%	6.4%
150	3%	3.1%
150	2%	2.7%

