## **14 ETHICAL AND REGULATORY CONSIDERATIONS**

### **14.1 IRB/EC Approval**

Sponsor or designees must submit the study protocol, Informed Consent Form (if applicable), and all other locally required documentation to an appropriate IRB/EC and obtain study-specific written approval (favorable opinion) before Investigators being allowed to participate in the study. Before commencement of the study, the Investigator or designee must provide the Sponsor with written documentation of such approval. The IRB/EC must give written renewal of the original approval at least annually to continue the study, if applicable per local regulation. In this case, a copy of the written renewal must be provided to the Sponsor.

The IRB/EC will be notified of any amendments to the protocol, as well as possible associated information and consent form changes, where applicable, and written approval (favorable opinion) will be obtained prior to implementation, as applicable.

The Investigator or designee is responsible for fulfilling any conditions of approval imposed by the IRB/EC, such as regular safety reporting, study timing, etc. The Investigator or designee will provide the Sponsor with copies of such reports.

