5.2 Analysis Methods

5.2.1 Primary Performance Endpoints

5.2.1.1 Performance of the BD Spinal NRFit™ Needle and BD NRFit™ Introducer

- Rate of successful BD Spinal NRFit™ Needle placement

The successful placement of the BD Spinal NRFit™ needle in the subarachnoid location is defined as the spontaneous appearance of cerebrospinal fluid (CSF) emerging from the spinal needle hub. In case of multiple attempts, successful placement is determined by the last attempt.

It will be computed as the number of participants experiencing the event divided by the total number of subjects with needles attempted; 95% confidence interval (exact method) will be calculated. The analysis will be performed on the treated population as defined in section 4.1.

The incidence of successful needle placement will be based on counts of "Yes" response to the following question on the "Spinal Procedure Details - BD NRFit Needle" CRF page: "Was there a spontaneous appearance of cerebrospinal fluid (CSF) emerging from the needle hub?"

- Rate of successful BD Spinal NRFit™ Needle placement when a BD Spinal NRFit™ Introducer is used

The successful placement of the BD Spinal NRFit™ needle in the subarachnoid location is defined as the spontaneous appearance of cerebrospinal fluid (CSF) emerging from the spinal needle hub for subjects who used BD NRFit™ introducer. In case of multiple attempts, successful placement is determined by the last attempt. If a subject uses BD NRFit™ introducer for the last attempt, the subject will be considered as part of the introducer population.

The incidence rate for the primary performance endpoints will be calculated as the number of participants experiencing the event divided by the total number of treated participants using BD NRFit™ introducer; 95% confidence interval (exact method) will be calculated.

A subject will be included in the analysis population if both of the following two conditions are met:

- Spinal Procedure CRF page: 'Was spinal procedure performed or attempted using BD NRFit devices?' Equals 'Yes'

THIS SUBJECT MATTER IS RESTRICTED SOLELY FOR THE USE OF BECTON DICKINSON AND COMPANY AND ITS SUBSIDIARIES

 BD	Statistical Analysis Plan	Page No.
	Study ID: MDS-21NRFit001	8 of 13

GFM-10082C

- AND

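### Three of the five planned precision figures (4.8%, 6.0%, 6.4%) are not exact-method half-widths, although the other two rows are and every primary analysis uses the exact method

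*SAP*

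**What the plan says.** SAP section 2.4 and Protocol section 10.2 plan about 150 participants for the needle and syringe and "approximately 100 subjects treated with BD NRFit™ Spinal Introducer". Both give the reason for that size: "The sample size is based on the precision of endpoint estimates as well as the ability to detect adverse events".

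The precision part is a five-row table (SAP Table 2, Protocol Table 1) of half-widths of the 95% confidence interval: 4.8% (n = 150, rate 90%), 6.0% (n = 100, 90%), 6.4% (n = 150, 80%), 3.1% (n = 150, 3%) and 2.7% (n = 150, 2%). The text repeats the first two rows, beginning "For a given endpoint with 90% rate, a sample size of 150 would lead to a precision of 4.8" per cent. Neither document names the interval method in the sample size section.

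The analysis sections do name one. For needle and introducer placement, SAP section 5.2.1.1 says "95% confidence interval (exact method) will be calculated". For syringe aspiration, section 5.2.1.2 has the count "divided by the total number of treated participants using the BD NRFit™ Syringes; 95% confidence interval (exact method) will be calculated". The other syringe endpoints, the headache endpoint and the related adverse events (SAP 5.2.1.2 and 5.2.2; Protocol 10.5.1 and 10.5.2) all specify the exact method too.

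**The concern.** A planning table that supports an exact analysis should contain exact half-widths, or say that it does not. Here one column under one heading appears to hold two kinds of figure, and the rows that depart from the planned analysis are the more favourable ones.

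The rows carry no endpoint labels. Matched by rate and sample size to the acceptance criteria in SAP section 1.3, the affected rows are needle placement (at least 90%), introducer placement (90%, n = 100) and the criterion "Incidence of aspiration/injection through a BD NRFit™ syringe" (above 80%).

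At stake is the accuracy of the stated basis for the sample size. Someone who takes 4.8% at face value expects a lower limit of 90 − 4.8 = 85.2% at an observed 90%. The planned analysis would give 84.0%. For the introducer row the contrast is 84.0% expected against 82.4% delivered.

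**Working it through.** **Inputs.** The sample sizes, rates and stated half-widths come from SAP section 2.4, and the exact method from SAP sections 5.2.1 and 5.2.2. Intervals are taken as two-sided 95%, so z = 1.96. The event count is x = n × p: 135, 90, 120, 4.5 and 3 for the five rows.

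**Formulas for the half-width.**
- Wald: z√(p(1−p)/n).
- Wilson: [z/(1 + z²/n)] × √(p(1−p)/n + z²/(4n²)).
- Exact (Clopper-Pearson): half of (U − L), where L is the 2.5% quantile of Beta(x, n−x+1) and U is the 97.5% quantile of Beta(x+1, n−x).

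**Reproducing the plan's first figure.** Wald at n = 150, p = 0.90 is 1.96 × √(0.09/150) = 1.96 × 0.02449 = 4.80%. Wilson gives 4.84%. Both round to the stated 4.8%. The exact interval for 135/150 is 84.04% to 94.29%, with half-width (94.29 − 84.04)/2 = 5.13%.

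**All five rows (half-widths in %).**

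| n, rate | Stated | Wald | Wilson | Exact |
|---|---|---|---|---|
| 150, 90% | 4.8 | 4.80 | 4.84 | 5.13 |
| 100, 90% | 6.0 | 5.88 | 5.96 | 6.36 |
| 150, 80% | 6.4 | 6.40 | 6.37 | 6.69 |
| 150, 3% | 3.1 | 2.73 | 2.94 | 3.12 |
| 150, 2% | 2.7 | 2.24 | 2.52 | 2.66 |

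The first three rows match Wilson to one decimal and miss the exact value. Wald fits the two n = 150 rows but gives 5.9% at n = 100. A mid-P interval (4.84, 5.95, 6.40) fits all three. The last two rows match the exact value and miss Wald and Wilson. Other constructions were tried, including Agresti-Coull, Jeffreys, likelihood ratio, logit, Blaker, Sterne and continuity-corrected forms. None gives all five rows. The nearest is logit, at 4.9, 6.1, 6.4, 3.1 and 2.7.

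**Size of the gap, exact against stated.**

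| n, rate | Exact 95% CI | Exact − stated (points) | Relative to stated | Reach below the rate (points) |
|---|---|---|---|---|
| 150, 90% | 84.0–94.3% | 0.33 | 6.8% | 5.96 |
| 100, 90% | 82.4–95.1% | 0.36 | 6.0% | 7.62 |
| 150, 80% | 72.7–86.1% | 0.29 | 4.6% | 7.30 |

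The table is given to 0.1 point, so rounding does not explain gaps of 0.29 to 0.36. The last column shows that the exact intervals are asymmetric and extend further on the unfavourable side.

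**Scale only.** The smallest n whose exact half-width (with x = n × p) is at or below the stated figure is 170 (4.797%), 112 (5.987%) and 164 (6.390%). The plan sets no target precision, so these are not shortfalls.

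**The other figure in that section.** The 77.9% chance of seeing at least one event with a 1% rate is right: 1 − 0.99^150 = 77.85%.

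**The case against.** The strongest reply is that nothing turns on these numbers. There is no hypothesis test, no power calculation and no target width. The acceptance criteria are not tied to a confidence limit, and the size is also supported by the adverse-event calculation, which is correct. All of that stands, and it limits the weight of the point.

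Second, the intervals will be wider than stated only if the observed rate equals the tabulated one. The tabulated rates match the acceptance floors, and higher rates give narrower exact intervals: 137/150 (91.3%) has a half-width of 4.83% and 138/150 (92%) has 4.68%. The 150 is also a minimum number of treated participants. This is true of what may be observed, but the table states half-widths at 90% and 80%, and at those rates they are not the exact ones.

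Third, the choice of method is inferred, because the documents name none. An approximation for common rates and an exact interval for rare ones might have been deliberate: the first three rows expect at least 10 events and 10 non-events, the last two fewer than 5 events. No text supports that reading, and the table would still need the label. Logit comes within 0.1 of every row but gives 4.9 and 6.1 for the first two, so it does not rescue the table.

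Fourth, the 3% row equals the exact figure only at the non-integer count 4.5; counts of 4 and 5 give 2.98% and 3.26%. This is fair, and a footnote would deal with it.

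**Conclusion.** The point holds. At the stated rates and sample sizes, the planned exact method gives half-widths of 5.1%, 6.4% and 6.7%, against 4.8%, 6.0% and 6.4% in both documents. The understatement is 0.3 to 0.4 points, or 5 to 7% in relative terms. The 3.1% and 2.7% rows already agree with the exact method.

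The conclusion assumes two-sided 95% intervals, exact read as Clopper-Pearson, and a count equal to n × p. That the first three rows came from Wilson or a similar approximation is an inference from recomputation; that they differ from the Clopper-Pearson half-widths does not depend on it. Since one heading covers all five rows and no single method tried yields them all, at least some rows are wrong or unlabelled whichever method was intended. The analysis sections settle which ones to change.

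The consequence is modest. The reported intervals will be valid and no decision rule changes. The correction should be made because these figures are given as a basis for the sample size.

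**What to change.** In SAP section 2.4 and Protocol section 10.2:

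- Restate the three rows as 5.1% (84.0–94.3%), 6.4% (82.4–95.1%) and 6.7% (72.7–86.1%). Printing the limits shows the asymmetry that a half-width hides.
- Correct the sentence that repeats the 90% figures to 5.1% and 6.4%.
- Keep 3.1% and 2.7%, with a footnote that the 3% row uses the notional count 4.5.
- Name the method in the column heading, for example: half-width of the exact (Clopper-Pearson) 95% CI.

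Enrolment and the analyses stay as they are. The cost is a text and table correction in two documents and slightly less favourable stated precision. On the protocol side it is an amendment, and Protocol section 14.1 provides that "The IRB/EC will be notified of any amendments to the protocol".
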